#### **End dates of concomitant and subsequent anti-tumor therapy are missing**

If the end date of concomitant and subsequent anti-tumor therapy is missing, the rules for filling it in follow:

- 1) If only "day" is missing for the end date, fill in the last day of the month of the end date or the date of death (for deceased subjects) as the day part, whichever is earlier
- 2) If the "month" and "day" are both missing from the end date, fill in December 31 of the year of the end date or the date of death (for deceased subjects), whichever is earlier,

as the “month” and “day” parts

3) If the “year,” “month,” and “day” of the end date are all missing, do not fill them in  
**The date of death is missing**

For subjects who are confirmed dead, if the complete date of death cannot be known, use the date of death after filling it in or the known last date of survival + 1, whichever is later, as the date of death. The rules for filling in the date of death are as follow:

- 1) If only the “day” is missing, fill in the 1st date of the month;
- 2) If “month” and “day” are missing, fill in January 1 of the year.

Other missing time data are not processed.

**Note:** In the data list, listing is still based on the original collected data.

### **2.2.9. Impact of the COVID-19 Epidemic**

The COVID-19 epidemic has had a certain impact on data collection during the trial and subsequent statistical analysis. The COVID-19 epidemic may cause subject tumor efficacy evaluations to be regarded as “missing” or “NE” in planned visits. When handling the efficacy data, it is treated as “missing” in accordance with established event censorship rules. This handling method is relatively conservative in the estimation of PFS.

For subjects whose evaluation results before progression as “NE” because of the epidemic, sensitivity analysis will be performed on the date when PFS is censored to the final assessment result of “NE” before disease progression.

For safety variables, descriptive summarization is performed based on the analysis visit window.

The COVID-19 epidemic also has an impact on the execution of clinical studies. Serious protocol deviations have occurred because of the epidemic. Therefore, this study will separately summarize the included and excluded serious protocol deviations caused by the epidemic.

If there are other conditions affected by the epidemic, they will also be analyzed.

## **2.3. Statistical analysis set**

Screened subjects are patients who signed the informed consent form and participated in the screening process of this study. Random subjects are patients who received randomization and were assigned random numbers.

### **2.3.1. Full analysis set (FAS)**

Based on the principle of intention-to-treat (ITT), the FAS is defined as all patients who were randomly enrolled and received the investigational drug treatment at least once. Comparisons between treatment groups will be based on the randomized grouping results, regardless of whether the group’s drug treatment was actually received.

### **2.3.2. Per protocol set (PPS)**

As a subset of the FAS, the PPS is defined as all of the patients who satisfied the trial protocol, had good compliance, and did not have serious protocol deviations that significantly affected efficacy evaluation.

Baseline and demographic characteristics will be analyzed using the FAS and the primary efficacy evaluation will be based on the FAS and the PPS simultaneously, with results being obtained primarily from the FAS.

### **2.3.3. Safety set (SS)**

The safety set (SS) will include all randomized patients who received the investigational drug treatment at least once, but comparisons between treatment groups will be summarized based on the treatment group that was actually received. For example, for patients who receive the wrong treatment: The randomly assigned treatment group is A and treatment B is actually received. The safety data should be counted in group B. The safety evaluation will be performed based on the SS.

### **3. Subject information**

Unless specifically stipulated, all enrolled subjects undergo descriptive summarization based on randomized treatment group and in total.

#### **3.1. Failure in Screening**

The causes of subject screening failure are descriptively summarized. In the calculation of composition ratio, the number of subjects who signed the informed consent form is the denominator.

Subject screening failure is shown as a list.

#### **3.2. Condition of enrolled subjects**

The completion of enrolled and randomized subjects is descriptively summarized. In the calculation of composition ratio, the number of randomized subjects is the denominator.

The summarization of the number and percentage of subjects includes the following information:

- Subjects who received at least one study drug treatment
- Subjects still continuing the investigational drug treatment at the time of data cutoff
- Subjects who terminated treatment and reasons

The conditions of subjects who terminated treatment after enrolled and randomized are given in a list.

#### **3.3. Distribution of Subjects in Each Analysis Set**

The distribution of subjects in each analysis set is summarized based on all enrolled and randomized subjects. The numbers and percentages of subjects are summarized based on the reasons for exclusion from each analysis set. In the calculation of composition ratio, the number of randomized subjects is the denominator.

The descriptive summaries of the subjects enrolled in each analysis set will be performed based on treatment group and as a whole.

The conditions of subjects excluded from the FAS and PPS are given in a list.

A list of subjects with random stratification errors will be given.

#### **3.4. Protocol Deviations**

All serious protocol deviations in the randomized, double-blind treatment stage based on the FAS will be summarized by treatment group and as a whole.

Considering the impact of the epidemic, in addition, summaries of excluded serious protocol deviations due to the impact of the epidemic will be given.

All serious protocol deviations of subjects in the full analysis set are given in a list.

### **3.5. Demographic data and baseline characteristics**

The following demographic indicators and baseline characteristics are summarized based on the FAS and PPS by treatment group:

Age (years), height (cm), weight (kg), body mass index (BMI) (kg/m^2), age group (< 65, ≥ 65 years old), sex (male, female), ethnicity (Han, other), and smoking history (present, absent).

At the same time, the following baseline disease characteristics are summarized:

Pathological type (adenocarcinoma, squamous cell carcinoma, large cell carcinoma, other), diagnostic staging (IIIB, IV), relapse status (yes, no), ECOG PS score (0 points, 1 point), EGFR gene mutation type (Ex19del, L858R), T790M mutation (yes, no), and brain metastasis (yes, no).

The demographic data, the baselines, and the above baseline disease characteristics of all subjects are given in a list.

---

### **3.6. Past Medical History**

Subjects' past medical histories are coded with MedDRA 23.0 or a higher version.

Subjects' past medical histories are summarized and described based on the FAS by treatment group and system organ classification/preferred term (SOC/PT).

The details of all subjects' past medical histories are listed.

### **3.7. Ophthalmological examination, Surgical History, and Allergy History**

The ophthalmological examination results, surgical histories, and allergy histories of all subjects are given separately in lists.

### **3.8. Subject Exposure and Medication Compliance**

Exposure to and compliance with the investigational drug are summarized based on the safety set by treatment group.

Exposure time is calculated as follows:

Total exposure time (days) = (date of last dose - date of first dose) + 1;

Cumulative exposure time (days) = total exposure time - cumulative number of days without medication;

Medication compliance = cumulative exposure time / total exposure time \* 100%;

The details of subject medication are listed.

### **3.9. Past and concomitant medications**

In this study, past medications and concomitant medications will be coded with WHO Drug 2020Q1 or a newer version.

Past medications are non-investigational drugs whose medication start dates are before the first medication.

Concomitant medications are drugs that started to be taken after the first medication or were taken before the first medication but continued to be used subsequently.

For past and concomitant medications, the frequencies and percentages of subjects by treatment group based on the coded ATC3 category and ATC1 category, ATC3 and preferred term are given separately.

The past and concomitant medications of all subjects are given in a list.

### **3.10. Concomitant and Subsequent Anti-Tumor Therapies**

The concomitant and subsequent anti-tumor therapies in this study will be coded with WHO Drug 2020Q1 or a higher version.

Concomitant anti-tumor therapies are other anti-tumor therapies used during medication with the investigational drug.

Subsequent anti-tumor therapies are other anti-tumor therapies used after the last use of the investigational drug.

The frequencies and percentages of concomitant and subsequent anti-tumor therapies are descriptively summarized by treatment group and coded ATC3 category.

The concomitant and subsequent anti-tumor therapies of all subjects are given in a list.

#### 4. Analysis of efficacy

##### 4.1. Primary Efficacy Endpoint Analysis

The primary efficacy endpoint of this study is PFS as evaluated by the investigator. The primary analysis is based on the full analysis set. For the rules for determining the dates of progression when the subjects have disease progression during treatment, see [Table 4.1-1](#). For the primary event censoring rules, see [Table 4.1-2](#).

Table 4.1-1 Rules for determining the date of progression when there is disease progression

	Description of situation	Outcome (occurrence of event or censoring)	Date of occurrence of PFS event or end date
Progression confirmed during treatment	New lesions	Progression	Date of imaging examination during which new lesions were first found (if the criterion for progression is new lesions)
	Non-target lesions	Progression	Date of last imaging examination during which progression of non-target lesions was first found
	Target lesions	Progression	Date of last imaging examination during which progression of target lesions was first confirmed
When two or more are present, the corresponding dates are determined based on the above principles and compared. Finally, the earliest examination date is taken as the date of disease progression			

Table 4.1-2 PFS event censoring rules 1 (primary event censoring rules)

Situation	Date	Outcome
No baseline or post-baseline imaging evaluation results	Date of randomization	Censored
No progression or death before data cutoff	Date of the last valid imaging examination before data cutoff	Censored
Treatment terminated or new systemic tumor therapy started before non-imaging disease progression	Date of the last valid imaging examination before the termination of treatment or the start of new systemic anti-tumor therapy	Censored
Disease progression or death before data cutoff (including occurrence during a missing visit or unplanned visit)	Examination date of first imaging disease progression or date of death	Progression or death

Progression or death occurred before data cutoff but two or more consecutive visits are missing or evaluation could not be performed before progression or death	Date of last valid imaging examination before progression or death	Censored
Note: No baseline is when there are no baseline examination records or baseline target lesion examinations are missing.		

The log-rank test stratified by EGFR mutation type and brain metastasis status will be used to compare the PFS distributions of the HS-10296 group and the gefitinib group to determine whether there are statistical differences. This test is a two-tailed test with a level of significance of 0.05. The results will be given as test p values.

Kaplan-Meier plots of the two treatment groups are drawn and the 1/4 quantile, median value, and 3/4 quantile of the PFS of the two treatment groups as well as the 95% confidence intervals for each quantile are given. The Kaplan-Meier estimates of progression-free survival at 6, 12, 18, and 24 months as well as the 95% confidence intervals corresponding to the K-M estimates based on Greenwood's standard error estimation method are given.

The stratified Cox proportional hazards model is used to estimate the PFS hazard ratio (HR) of the two treatment groups and the 95% confidence intervals corresponding to the estimates are given. The reasonableness of the proportional hazards assumption in this model will be tested.

The above two tests use subjects' actual stratification information during the screening period for analysis.

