### 1.3. Endpoint indicators

#### 1.3.1. Primary efficacy indicators

The primary endpoint of this study is PFS derived by the investigator based on the RECIST V1.1 evaluation ratings. PFS is defined as the time from the start of randomization until objective tumor progression as evaluated by the investigator or death (using the date of the first event).

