### **2.2. General principles and analytical definitions**

The biostatistician and principal investigator formulate the statistical analysis plan, which is finalized before data are locked, based on the study protocol.

- 1) For the time interval, days are converted into months at one month = 30.4375 days.
- 2) Efficacy analysis is performed in the full analysis set (FAS) and the per-protocol set (PPS). The results are based on the full analysis set. Safety analysis is performed in the safety set (SS).
- 3) Except for special circumstances, the statistical diagrams are only for planned visit points, while the data sheets list all visits, including unplanned visits.

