#### 2.2.8.1. Main efficacy data

The primary endpoint of this study is the time outcome variable. When tumor efficacy assessment results are missing from a visit point, refer to [Table 4.1-2](#) and [Table 4.2-1](#) for the handling rules.

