#### 4.2. Sensitivity Analysis of the Primary Efficacy Endpoint

The following sensitivity analysis is performed on the primary efficacy endpoint:

- Considering the presence of primary resistance to EGFR TKI in non-small cell lung cancer patients with sensitive EGFR mutations, the early progression data may not satisfy the statistical assumptions of proportional hazards. The primary event censoring rules will be adopted to analyze the data of patients with primary drug resistance removed from the primary efficacy endpoint (progression within 3 months) in the full analysis set
  - The primary event censoring rules are used for analysis of the main efficacy endpoint in the per-protocol set
    - The primary event censoring rules are used for analysis of the main efficacy endpoint minus 42 days of patients with disease progression after 15 months in the full analysis set
    - The primary event censoring rules are used for re-analysis of the main efficacy endpoint based on the full analysis set
  - The primary event censoring rules are used for analysis of the PFS results derived by IRC evaluation based on the full analysis set
  - Based on the primary event censoring rules, subjects for whom the main efficacy endpoint is evaluated as "NE" before progression because of the epidemic are censored to the date on which the evaluation result before disease progression is "NE" for sensitivity analysis

Table 4.2-1PFS event censoring rules 2 (secondary event censoring rules)

Situation	Date	Outcome
No baseline or post-baseline imaging evaluation results	Date of randomization	Censored

No progression before data cutoff	Date of the last valid imaging examination before data cutoff	Censored
Progression or death before data cutoff	Examination date of first imaging disease progression or date of death	Progression or death

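### Row 1 of both PFS censoring tables has no exception for death, so a death before the first post-baseline scan is both censored and an event; Table 4.2-1 row 2 also omits death

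*SAP*

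**What the plan says.** **Endpoint.** SAP 1.3.1 states that "PFS is defined as the time from the start of randomization until objective tumor progression as evaluated by the investigator or death", with the first event fixing the date. Protocol 12.1.3 has the same two components and censors a death only when it follows two or more missing visits. SAP 2.2 describes the plan as "finalized before data are locked, based on the study protocol".

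**Table 4.1-2 (SAP 4.1, primary rules).**
- Row 1: "No baseline or post-baseline imaging evaluation results". Censored at randomization.
- Row 2: neither progression nor death by cutoff. Censored at the last valid imaging.
- Row 4: "Disease progression or death before data cutoff (including occurrence during a missing visit or unplanned visit". Event, dated at first imaging progression or at death.
- Row 5: progression or death, but "two or more consecutive visits are missing or evaluation could not be performed before progression or death". Censored at the last valid imaging before it.
- The note under the table says only what counts as having no baseline.

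**Table 4.2-1 (SAP 4.2, secondary rules).** Row 1 is worded as above. Row 2 censors subjects without progression by cutoff and does not mention death. Row 3, "Progression or death before data cutoff", is an event. There is no missed-visit row.

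**Missing assessments.** SAP 2.2.8.1 says: "When tumor efficacy assessment results are missing from a visit point, refer to" Tables 4.1-2 and 4.2-1. Neither that section nor SAP 2.2.9, 4.1 or 4.2 says which row governs when two apply.

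**The concern.** The first post-baseline tumor assessment is due at week 6. Anyone who dies before it has no post-baseline imaging and so meets row 1, but also meets the death row. The two outcomes are opposite: no follow-up time and no event, or an event on the day of death. A program that works down the table in order reaches row 1 first.

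This is the primary endpoint, and the patients concerned are those with the worst outcome. If early deaths differ between arms, removing them favours the arm that has more. The planned sensitivity analyses would not show it. The per-protocol and IRC analyses use the primary rules, and the secondary-rule analysis (output 14.2.4 in SAP section 7) has the same row 1.

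**Working it through.** **1. One patient, all rules.** Baseline scan present, death on day 30, no post-baseline scan, before cutoff.

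| Source | Result |
|---|---|
| Table 4.1-2 row 1 | Censored, day of randomization |
| Table 4.1-2 row 4 | Event, day 30 |
| Table 4.2-1 row 1 | Censored, day of randomization |
| Table 4.2-1 row 2, read literally | Censored, last valid imaging |
| Table 4.2-1 row 3 | Event, day 30 |
| SAP 1.3.1 | Event, day 30 |
| Protocol 12.1.3 | Event; no tumor assessment yet missed |

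The definition and the protocol agree with the death rows. Table 4.2-1 row 2 reaches further: read literally, it overlaps row 3 for every death without progression, scanned or not.

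**2. The plan's own figure.** Inputs from protocol 5.3: HR 0.67, two-sided alpha 0.05, power 90%, 1:1. Schoenfeld: 4(1.960 + 1.282)² / (ln 0.67)² = 262.06, against 262 stated. Power at 262 events is 0.8999. With medians of 10 and 15 months, A = 8 months of uniform accrual and T = 23 months in total, the event probability per arm is 1 − [exp(−λ(T−A)) − exp(−λT)]/(λA), with λ = ln 2/median. This gives 0.729 and 0.582, mean 0.655, so 410 × 0.655 ≈ 269 events. The planned numbers reproduce and do not depend on row 1.

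**3. Size of the miscoding.** The documents give no early-death rate, so the splits below are assumptions. Exponential PFS and accrual as in step 2; early deaths uniform over days 1–42, at deaths/205 per arm; unstratified Cox HR from 1,000,000 simulated patients per arm. The SE of log HR is 2/√262 = 0.1236.

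| Early deaths, HS-10296 vs gefitinib | HR, counted | HR, censored at day 0 | Shift in log HR | Shift / SE |
|---|---|---|---|---|
| 2 vs 2 | 0.672 | 0.668 | 0.006 | 0.05 |
| 4 vs 4 | 0.675 | 0.667 | 0.011 | 0.09 |
| 4 vs 2 | 0.684 | 0.668 | 0.023 | 0.19 |
| 6 vs 2 | 0.695 | 0.667 | 0.041 | 0.33 |
| 8 vs 2 | 0.708 | 0.668 | 0.058 | 0.47 |
| 0 vs 4 | 0.650 | 0.665 | −0.023 | −0.19 |
| 2 vs 6 | 0.655 | 0.667 | −0.018 | −0.15 |

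**4. Power.** If 0.5% to 3% of 410 die this early (2 to 12 patients) and all are removed from 262 events, power falls from 90.0% to between 89.8% and 88.6%.

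**The case against.** **Row 1 may mean that neither kind of imaging exists.** A patient with the mandatory baseline scan would then fall outside it. The wording allows this, but the note under Table 4.1-2 defines having no baseline as a condition on its own, which favours the either/or reading. Under the neither reading, a living patient with only a baseline scan would be censored under row 2 at a date before randomization. That reading would also leave Table 4.2-1 row 2 uncorrected.

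**The intent is plain, and few such deaths are expected.** Both parts stand. The definition and the protocol point to event coding, and entry requires ECOG 0–1 and at least 12 weeks' expected survival. The 8 versus 2 split means 8/205 = 3.9% of one arm dead within 42 days. This limits the importance of the point but does not make the written rule correct.

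**Stronger readings that a reader might infer.**
- That row 3 of Table 4.1-2 ("Treatment terminated or new systemic tumor therapy started before non-imaging disease progression") also censors a patient who stops drug and then dies. The row does not mention death. How discontinuation is handled is a separate question.
- That the closing words of row 5 on non-evaluable assessments, taken alone, cover a scan not yet due. The natural reading is that two or more consecutive visits governs both halves of the phrase.
- That missed clinic visits in cycle 1 are enough to trigger row 5. SAP 2.2.8.1 and 2.2.9 speak of tumor assessments missing at planned visits, and C1D8 and C1D15 have none.

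**Conclusion.** Wrong as written, but small: minor to should-fix. For a death before the first post-baseline scan, row 1 of both tables contradicts the death row, the SAP's endpoint definition and protocol 12.1.3. Row 2 of Table 4.2-1 adds a wider overlap through an omitted reference to death. SAP section 6 lists only the change to the OS definition, so nothing marks either row as a deliberate departure.

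Under the assumed splits, the HR shift is below 0.01 when early deaths are balanced and about half an SE of log HR in the most unequal case tried. These sizes rest on assumed death counts, exponential PFS and an unstratified model. The conflict between the rows needs none of those assumptions.

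A reader might infer that the primary result or the sample size is in doubt. The documents do not support that: no early-death imbalance is given, OS is not governed by these tables, and 262 events and 410 patients stand.

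**What to change.** 1. **Row 1, both tables.** Add: *except that a subject with no post-baseline imaging who dies before data cutoff is handled by the death rows*. Limiting the exception in this way leaves a no-baseline subject with later imaging progression as now. An unrestricted clause would make that subject's earlier progression count only if he or she later died.
2. **Table 4.2-1, row 2.** Insert *or death* after progression, to match row 2 of Table 4.1-2. Row 3 then counts these deaths as events at the date of death.
3. **Table 4.1-2, rows 4 and 5.** State that a death before two consecutive scheduled tumor assessments have been missed is an event at the date of death (row 4). State that a later death with no post-baseline imaging stays censored under row 5, with randomization as the censoring date. The only valid scan then is the baseline scan, taken up to 28 days before treatment starts on the day of randomization, and using its date would give a zero or negative PFS time. Define visits in row 5 as scheduled tumor assessments, consistent with SAP 2.2.8.1 and 2.2.9.

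Row 3 needs no change for this point. The cost is a few words in two tables and the matching program lines, with no change to data collection, event target or sample size.

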12.1.3 Progression-free Survival (PFS)

According to RECIST 1.1 ([Appendix D](#)), PFS is defined as the time period from the randomization to the occurrence of objective tumor progression assessed by the Investigator or death. In the absence of disease progression, radiographic tumor assessments will need to be collected until RECIST-defined disease progression, even if the patient has discontinued the treatment with HS-10296 or has received another anti-tumor therapy prior to disease progression.

A subject who does not have disease progression or is dead at the time of analysis will be censored at the last date of his/her last assessment as per the RECIST criteria. If a subject

experiences disease progression or death after 2 or more missing visits, the subject will be censored at the last date of his/her last assessment as per the RECIST criteria. The data derived from the progression-free survival are based on assessment date rather than visit date.

If a patient discontinues study treatment prior to progression and/or receives other treatments prior to progression, the patient will be continued to be followed up until evidence of objective disease progression as per RECIST 1.1. Worsening of symptoms will not be considered as an event of progression.

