4.5 Worsening of Symptoms

Symptomatic deterioration is not a descriptor of an objective response, rather, it is a reason for discontinuation of study treatment. Patients with "symptomatic deterioration" who require discontinuation of study treatment but show no objective evidence of disease progression should continue to be assessed as per RECIST 1.1 according to the clinical study protocol until objective disease progression is observed.

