##### **Progression follow-up for subjects who terminate treatment for reasons other than disease progression:**

- Solid tumor efficacy evaluation is performed once every 6 weeks (C1-C21) or 12 weeks (C23 and after) until the investigator evaluates disease progression based on RECIST 1.1
- ECOG PS scoring is performed once every 6 weeks (C1-C21) or 12 weeks (C23 and after) until the investigator evaluates disease progression based on RECIST 1.1
- Recording of concomitant medications: Only the detailed information of subsequent anti-tumor treatment is recorded until disease progression
- Subjects with disease recurrence before the completion of the 28-day safety follow-up after discontinuation of treatment should continue the safety follow-up until 28 days after discontinuation of treatment.

**Progression follow-up of subjects who continue to receive the investigational treatment (compassionate treatment) after disease progression:**

- It is recommended to conduct tumor evaluation based on RECIST 1.1 once every 6 weeks (C1-C21) or 12 weeks (C23 and after) until the investigator judges progression after compassionate treatment or medication is terminated before progression (for safety reasons or based on the investigator's judgment or the subject's decision)
- ECOG PS scoring is performed once every 6 weeks (C1-C21) or 12 weeks (C23 and after) until the investigator judges further progression or medication is terminated before progression (for safety reasons or based on the investigator's judgment or the subject's decision)
- Recording of concomitant medications: All concomitant medications, including anti-tumor therapy, until 28 days after the drug is terminated, after which only anti-tumor therapy is collected
- Recording of adverse events: For subjects who continue to receive the investigational treatment after progression, continue to collect their AEs and SAEs until 28 days after the drug is terminated, after which only AEs with no outcome and SAEs related to the investigational drug are collected.

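### The SAP's primary PFS rules censor at treatment stop or new therapy, which the protocol does not do; the rule overlaps the event rule with no stated precedence and is not declared as a change

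*SAP*

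**What the plan says.** **Protocol 12.1.3** censors PFS in two situations: no progression or death at the time of analysis, and progression or death after two or more missed visits. For a patient who stops treatment or receives other treatment before progression, it says "the patient will be continued to be followed up until evidence of objective disease progression as per RECIST 1.1". It adds: "Worsening of symptoms will not be considered as an event of progression". Appendix D 4.5 says that patients who stop for symptomatic deterioration "should continue to be assessed as per RECIST 1.1 according to the clinical study protocol until objective disease progression is observed". Protocol 6.1, 7.11 and 9.1.3.3 require the same follow-up, and SAP 1.2.2.3.3 repeats it: scans continue "until the investigator evaluates disease progression based on RECIST 1.1".

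**SAP Table 4.1-2** (primary censoring rules) has two rows that matter here:

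- Row 3, outcome censored: "Treatment terminated or new systemic tumor therapy started before non-imaging disease progression". The date used is "Date of the last valid imaging examination before the termination of treatment or the start of new systemic anti-tumor therapy".
- Row 4, outcome event: "Disease progression or death before data cutoff (including occurrence during a missing visit or unplanned visit".

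**SAP 4.2** lists the sensitivity analyses. One bullet reads: "The primary event censoring rules are used for re-analysis of the main efficacy endpoint based on the full analysis set". Table 4.2-1, which follows, is captioned as the secondary censoring rules, and output 14.2.4 in SAP section 7 is an analysis under those secondary rules.

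**SAP section 6** declares one change from the protocol, the start date for OS.

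**The concern.** Row 3 is a third censoring rule for the primary endpoint, and it sets aside events that the protocol takes care to collect. It also leaves the primary analysis undetermined. A patient who stops for an adverse event and later has imaging progression, or dies, satisfies row 3 (censored) and row 4 (event). The only tie rule in SAP 4.1 concerns progression dates in Table 4.1-1. Two competent programmers could produce different primary p values and hazard ratios from the same data.

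Such patients will occur: protocol 7.10 lists adverse events, poor compliance and need for other treatment among the reasons for withdrawal. Equal stopping rates cannot be presumed, since a reduced-dose kit exists for one arm only. If row 3 prevails, the censoring may be informative. DoR takes its end date from PFS, so it inherits the problem.

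**Working it through.** **1. Possible meanings of row 3.** The words about non-imaging progression are unclear. Three readings are possible:

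- *Any stop or switch without imaging progression.* A later scan progression or death meets rows 3 and 4.
- *Only a stop or switch linked to clinical progression.* Fewer patients are affected, but a later scan progression or death still meets both rows.
- *Only a date rule for patients who stopped and never had an event.* No event is lost. But row 2 already covers these patients with a different date (last valid scan before cutoff), and the table does not state this limit.

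Under each reading the rule is absent from protocol 12.1.3.

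**2. Whether a planned analysis follows the protocol rule.** Read literally, the SAP 4.2 bullet repeats the primary analysis. The Table 4.2-1 caption and output 14.2.4 show that the secondary rules were meant. Those rules omit row 3, but they also omit the missed-visit rule. In addition, their row for patients without progression does not mention death, so a death without progression fits both that row and the event row. No planned analysis clearly implements 12.1.3 or isolates the effect of row 3.

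**3. The plan's own figure.** Inputs from protocol 5.3: HR 0.67, medians 10 and 15 months, 1:1 allocation, 8 months' accrual, 23 months in total, two-sided 0.05, 90% power, 262 events, 410 patients.

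- Schoenfeld events: 4(1.960 + 1.282)² / (ln 0.67)² = 262.06. This reproduces 262.
- Event probability by month T with uniform accrual over A months: 1 − [exp(−λ(T−A)) − exp(−λT)] / (λA), with A = 8 and T = 23. For λ = ln 2/10 this is 0.7286; for λ = ln 2/15 it is 0.5820.
- Expected events: 205 × 0.7286 + 205 × 0.5820 = 149.4 + 119.3 = 268.7.
- Power at D events: Φ(½√D·|ln 0.67| − 1.960). At D = 268.7 this is 90.7%.
- 262 events are reached at month 22.2.

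**4. If row 3 prevails.** The stopping rates are assumptions. Add an exponential stopping hazard g, equal in both arms, with the progression hazard unchanged after stopping. The event probability becomes [λ/(λ+g)] × {1 − [exp(−(λ+g)(T−A)) − exp(−(λ+g)T)] / ((λ+g)A)}. Solve for g so that a given share of the 410 patients is censored by row 3 by month 23.

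| Share censored by row 3 | g per month | Counted events, month 23 | Events fitting rows 3 and 4 | Power at HR 0.67 | Month of 262nd counted event |
|---|---|---|---|---|---|
| 0% | 0 | 268.7 | 0 | 90.7% | 22.2 |
| 5% | 0.00448 | 259.5 | 9 | 89.7% | 23.3 |
| 10% | 0.00930 | 250.2 | 18 | 88.6% | 24.9 |
| 20% | 0.02016 | 231.0 | 38 | 86.1% | 30.7 |

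Counted events at month 23 fall below 262 once about 3.7% of patients (15 of 410) are censored this way. The documents do not say whether the cutoff is fixed in time or set by events. In the first case the cost is power; in the second it is time.

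**5. Effect on the hazard ratio.** Under equal, non-informative stopping the HR is 0.67 either way. A simulation assumed that the progression hazard doubles after stopping and that 12-month stopping rates are 5% on gefitinib and 15% on HS-10296. The HR was about 0.70 with later events counted and 0.67 under row 3. With the rates reversed it was 0.64 and 0.67.

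**The case against.** The strongest reply is that row 3 looks like a translation slip. Harm needs both a reading that covers patients with later events and row 3 taking precedence, and the SAP states neither. The follow-up sections govern data collection, which is also compatible with using later scans only in a sensitivity analysis, so the direct conflict is with 12.1.3. SAP 2.2.8.1 names Tables 4.1-2 and 4.2-1 together, so the SAP 4.2 bullet is very probably a wording error and an analysis without row 3 is planned. All of this is fair. None of it settles which row governs the primary test, and the planned alternative is not the protocol's rule.

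The figures can also be challenged:

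- The overlap counts are upper values. They assume that every patient who stops is followed to an event or to cutoff, although some will withdraw consent, be lost, or be censored by the missed-visit rule anyway.
- Medians of 10 and 15 months imply HR 2/3. At that value power is 90.4%, 89.4% and 86.9%, about 256 events suffice for 90%, and that threshold is crossed at about 7.1% of patients (29). The 3.7% figure refers only to the stated 262 events.

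Both points are correct, and they make an already modest power loss somewhat smaller.

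Finally, row 3 is not the only departure from 12.1.3. Row 1 censors at randomization when there are no scans, so an early death can fit rows 1 and 4. Row 5 adds non-evaluable visits to missed ones. This is further reason to align the whole table. Censoring at new therapy can be a legitimate primary choice, but it has to be chosen openly.

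**Conclusion.** The concern holds and must be fixed before database lock. The SAP adds a primary censoring rule that the protocol lacks, words it ambiguously, lets it overlap the event rule without precedence, and does not declare it. These facts come from the text and need no assumption. The size of the effect does rest on assumptions, because the documents give no rates of stopping or switching before progression. On the illustrative range of 5% to 20%, power falls by about 1 to 5 percentage points at month 23 (90.7% to between 89.7% and 86.1%), or the 262nd event is delayed by about 1 to 8.5 months. The direction of any bias in the HR is unknown. The main defect is that the primary result depends on an unstated programming choice.

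**What to change.** 1. Remove row 3 from Table 4.1-2. State in row 4 that progression or death counts as an event even after treatment termination or new anti-tumor therapy, subject to the missed-visit rule. Keep the row 3 rule as a labelled sensitivity analysis.
2. If the sponsor prefers row 3 as primary, define exactly whom it covers, state its precedence over row 4, and declare and justify it in SAP section 6.
3. While the table is open, align rows 1 and 5 with protocol 12.1.3 or declare them, and say how a death without post-baseline scans is coded.
4. Correct the SAP 4.2 bullet so that it refers to the secondary censoring rules, and add death to the second row of Table 4.2-1.
5. Reconcile protocol Appendix D 4.1, which ends scans at treatment discontinuation, with sections 9.1.3.3, 10.2.1 and 12.1.3 and Appendix D 4.5.

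The cost is SAP wording before database lock and one clarifying line in Appendix D. The main protocol text already plans scans to RECIST progression, so no new data collection should be needed, provided sites have followed that text rather than Appendix D 4.1.
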